7.0 STATISTICAL ANALYSIS

This study is a parallel randomized control trial that will evaluate the impact of CGM versus a standard fingerprick protocol, between and within randomized groups. The primary analysis (Specific Aim 1a) will measure the intervention effect on six-month change in HbA1c. The quantitative secondary analyses will measure the withinpatient longitudinal change in glycemic variability among CGM patients (Aims 1b-d) as well as the intervention effect on hypoglycemic events, healthcare utilization and cost (Aims 1e, 2a-b) between randomized groups. Additionally, for each of these aims, we will conduct exploratory sensitivity analyses: measuring provider variability and its effect, as well as looking at patient-level heterogeneity of treatment effect (HTE) to describe

subgroups of patients in whom the benefit of CGM might be amplified or attenuated. Technical details are provided in Section 7.1 *Statistical Considerations*.

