- **Process for Aim 1b:** MAGE is a metric of glycemic variability that can be measured from CGM, but not from infrequent (daily) monitoring. Thus, among CGM patients only, we will measure the six-month longitudinal change in 24-hr average MAGE. Upon computing each CGM patient's daily MAGE, we will use patient-level hierarchical modeling (generalized linear mixed models) to estimate the overall sixmonth longitudinal trend in MAGE.

Specific Aim 1c: Measure longitudinal change in daily coefficient of variation (C_v) of blood glucose in CGM

- **Hypothesis for Aim 1c:** The patient-level daily C_v of blood glucose will decrease over six months of CGM.
- **Process for Aim 1c:** Like that of MAGE, C_v of blood glucose is a metric of glycemic variability that requires near continuous monitoring. Thus, among CGM patients only, we will measure the six-month longitudinal change in daily C_v of blood glucose using the standard equation: $C_v = \sigma/\mu$. Once we have computed each CGM patient's daily C_v of blood glucose, we will use patient-level hierarchical modeling (generalized linear mixed models) to estimate the overall six-month longitudinal trend in C_v of blood glucose. Additionally, we will report the patient- and group-level distributions in daily blood glucose extrema (i.e., minimum and maximum).

Specific Aim 1d: Measure longitudinal change in overall blood glucose range and “time in range” ($\max \text{Range} - \min \text{Range}$) in CGM

- **Hypothesis for Aim 1d:** The patient-level daily blood glucose range will decrease and time in range (which is defined by glucose levels from 70 to 180) will increase over six months of CGM usage.
- **Process for Aim 1d:** Again, like MAGE and C_v , the blood glucose range is a metric of glycemic variability that is most meaningful with near continuous monitoring. So, among CGM patients only, we will measure the blood glucose range for the i th day as $\text{Range}_i = \max \text{HbA1c}_i - \min \text{HbA1c}_i$, and then use patient-level hierarchical modeling (e.g., generalized linear mixed models) to estimate the overall six-month longitudinal trend in HbA1c range.

Specific Aim 1e: Measure the effect of CGM vs. the standard finger-prick protocol on frequency of hypoglycemic events

- **Hypothesis for Aim 1e:** The patient-level six-month reduction in frequency of hypoglycemic events will be greater among those randomized to CGM than that among those randomized to control.

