7.1 Statistical Considerations

The primary analysis (Aim 1a) will measure the intervention effect on the patient-level six-month absolute reduction in mean HbA1c. Since not all patients will have their final HbA1c test at six months exactly, we will estimate each patient's six-month reduction in HbA1c by interpolating/extrapolating from their assessments, given that their HbA1c levels were assessed on at least two occasions: baseline, and >3 months post baseline. Then, among patients with a sufficient number of occasions of HbA1c assessments, we will estimate their sixmonth HbA1c using generalized linear mixed models with patient-level random slopes and intercepts, with appropriate link function and distributional family [8]. The quantitative secondary analyses (Aims 1b-e, 2a-b) will use outcomes related to the longitudinal change in various metrics of glycemic variability (MAGE, C_v , range) as well as the frequency of hypoglycemic events, healthcare utilization, and cost. The secondary analyses will also use longitudinal data analysis to assess whether there is a significant reduction in glycemic variability over six months (Aims 1b-d) among those randomized to CGM, whether there is a significant reduction in hypoglycemic events over six months (Aim 1e) among those randomized to CGM, and to assess whether overall healthcare utilization and costs differ between randomized groups [9]. Accordingly, specific aims 1b-e will rely heavily on longitudinal data analysis within a multilevel/hierarchical framework [10], specifically using generalized linear mixed models. In the sensitivity analyses, provider variability will be accounted for using three-level (provider, patient, occasion), quasi-Bayesian generalized linear mixed models [11]. Finally, the sensitivity analyses exploring HTE will use generalized additive models (GAM) to identify subgroups of patients for whom CGM is likely to have a differential effect [12-13].

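### The search for subgroups that benefit more or less from CGM extends to Aims 1b–1d, which have no control patients and no off-device baseline, so no treatment effect or variation in one can be estimated there

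*Combined protocol and SAP*

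**What the plan says.** Section 7.0 sets out the primary Aim 1a, then Aims 1b–1d as within-patient change in the CGM arm, then Aims 1e and 2a–b as comparisons between arms. It goes on: "for each of these aims, we will conduct exploratory sensitivity analyses". One of these is the HTE analysis, whose purpose is to describe "subgroups of patients in whom the benefit of CGM might be amplified or attenuated".

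Section 7.1 gives the method: the HTE analyses "will use generalized additive models (GAM) to identify subgroups of patients for whom CGM is likely to have a differential effect". It does not exclude Aims 1b–1d, does not mention an arm-by-covariate term, and lists no candidate modifiers.

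Section 2.0 fixes the population for these aims. For Aim 1b, "among CGM patients only, we will measure the six-month longitudinal change in 24-hr average MAGE". For Aim 1c, "among CGM patients only, we will measure the six-month longitudinal change in daily C_v of blood glucose". Aim 1d is limited in the same way. Section 2.0 gives the reason for MAGE: it cannot be obtained from infrequent finger-prick readings. Section 3.3.2 excludes current CGM users, and no blinded or run-in wear period is described.

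**The concern.** A treatment effect is a contrast between CGM and no CGM, and its heterogeneity is the way that contrast changes with a covariate. Aims 1b–1d supply neither side of the contrast. There are no control patients, and every reading comes after CGM has started, so there is not even a before-and-after comparison within the patient. A GAM fitted to these data describes which patients' MAGE, CV or range moves more over six months. It cannot say whether CGM caused the movement.

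Sections 7.0 and 7.1 nevertheless attach the language of CGM benefit and differential effect to that output. Section 1.1 says assessing the impact on cost, care and utilization is critical before more sites are added, and Section 8.3 plans to share data for predictive models. A list of patients who supposedly benefit most could feed either use.

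**Working it through.** **No stated figure to reproduce.** The documents give no number for the HTE analyses and no variance for MAGE, CV or range. What follows rests on the wording and on null simulations with assumed inputs.

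**Inputs from the documents.** 125 enrolled with 20% attrition leaves 125 × 0.80 = 100 patients (Section 7.2). The allocation ratio is not stated; 1:1 is assumed, giving about 50 CGM patients. Follow-up is six months, taken as 180 days. Two-sided 0.05 is assumed, since no alpha is given.

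**Check 1: split at the baseline median, CGM effect zero.** Let the metric have SD 1 at baseline and at six months, with correlation r and no mean change. The expected change given baseline b is −(1 − r)b. The two halves of a normal baseline differ in mean by 2√(2/π) = 1.596 SD, so the high half appears to improve more by (1 − r) × 1.596 SD. With 50 CGM-only patients and 20,000 runs:

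| r (assumed) | Formula, SD | Simulated, SD | CGM-only contrast, p<0.05 |
|---|---|---|---|
| 0.5 | 0.80 | 0.78 | 84% |
| 0.7 | 0.48 | 0.47 | 60% |
| 0.8 | 0.32 | 0.31 | 43% |
| 0.9 | 0.16 | 0.16 | 24% |

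On the same null data with 100 patients in two arms, the arm-by-subgroup interaction averages about 0 and is significant in 4.8–5.1% of runs.

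**Check 2: a covariate that is not the baseline.** Suppose one subgroup improves by 0.3 SD whatever device it uses. The CGM-only contrast shows about 0.30 SD and is significant in 17–64% of runs for r from 0.5 to 0.9. The two-arm interaction again stays at about 0, with about 5% rejection. Differing background trends therefore mislead even without regression to the mean.

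**Check 3: daily data, closer to Aim 1c.** Assumed: 50 CGM patients, 180 days, no CGM effect, stable between-patient SD 5 CV points, daily noise SD 7, and slow fluctuation within the patient lasting 30–90 days; 1,500 trials per setting. The predictor is mean CV on days 1–14. The outcome is the patient's least-squares slope.

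| Setting | p<0.05 |
|---|---|
| Slow SD 2–3, days 1–14 also in the slope | about 39–65% |
| Slow SD 2–3, slope from day 15 | about 12–40% |
| Little or no slow fluctuation, days 1–14 also in the slope | about 20–22% |
| Little or no slow fluctuation, slope from day 15 | about 5% |
| Covariate unrelated to trend | about 5% |

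Part of the first row comes from the same daily noise entering both predictor and slope; the third row shows that overlap alone can do this. A larger stable SD lowers the rate: with stable SD 8 and slow SD 2 lasting 30 days, it is about 20% with overlap and 8% without.

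**Check 4: what a valid HTE analysis could detect.** With 100 patients in four cells of 25, the interaction's standard error is √(4/25) = 0.4 SD of the change. Power for an interaction of 0.8 SD is about Φ(0.8/0.4 − 1.96) = Φ(0.04) ≈ 52%. For 0.4 SD it is Φ(−0.96) ≈ 17%.

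**The case against.** The plan calls these analyses exploratory, aims only to describe subgroups where benefit might vary, and is open that Aims 1b–1d are within the CGM arm. It keeps the term intervention effect for Aims 1a, 1e and 2a–b. That limits the consequences. It does not supply the missing comparator: an exploratory label warns about multiplicity and low power, not about a quantity the data cannot yield.

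It can also be said that HTE was meant only for the randomized aims. The text reads otherwise, because the promise covers each aim just listed and 1b–1d are on the list. If the narrower scope was intended, the same short edit would say so.

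The point also shares its root with any caution about reading the main 1b–1d trend as a CGM effect. The edit is still separate, since describing the main trend as uncontrolled would leave the HTE promise in place.

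The strongest objection concerns size, and it stands. The plan names no modifiers. The high rates need the metric's own starting value as modifier, and the highest also need overlapping days. For age, diabetes type or clinic, regression to the mean arises only through correlation with error in the starting value; without that, the remaining threat is differing background trends. A reader might take 39–65% as the expected false-finding rate, and the documents do not support that.

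**Conclusion.** The plan is wrong as written on a secondary, exploratory matter. For Aims 1b–1d, neither a treatment effect nor its heterogeneity is identifiable. Observed subgroup differences in trend cannot be separated from background trends or, where the subgroup variable is the starting value or is correlated with its error, from regression to the mean. That conclusion needs no numerical assumption. The size of any spurious subgroup does: it depends on the modifier chosen, on whether its days overlap the slope, and on how much the metric drifts within a patient. Across the assumed daily-data settings it runs from the nominal 5% to about 65%.

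Three stronger readings are tempting and not supported:
- That all aims are affected. The sentence in Section 7.0 covers the quantitative aims; Aim 3 lies outside it.
- That any subgroup found in 1b–1d must be an artefact. Real differences in benefit may exist; these data cannot show them.
- That the trial's main result is compromised. Aim 1a is a randomized comparison and is untouched.

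Aim 1e belongs with the between-arm aims under Sections 2.0 and 7.0. Section 7.1 also speaks of a reduction in hypoglycemic events within the CGM group, and an HTE analysis run on that reading would share the problem.

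**What to change.** In Sections 7.0 and 7.1, limit HTE to the between-arm aims (1a, 1e, 2a, 2b) and state that it is estimated as an arm-by-covariate interaction, smooth where a GAM is used. For Aims 1b–1d, call the work exploratory predictors of trend within the CGM arm and remove the wording on CGM benefit and differential effect. If the metric's own starting value is examined, fit the slope on later days that do not overlap it, and report the result with a regression-to-the-mean caveat.

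The edit is about two sentences, with no new data and no change to the primary analysis. The price is fewer subgroup claims. Those that remain will be imprecise, since interactions at 100 patients have low power, and the report should say so.

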7.1 Statistical Considerations

The primary analysis (Aim 1a) will measure the intervention effect on the patient-level six-month absolute reduction in mean HbA1c. Since not all patients will have their final HbA1c test at six months exactly, we will estimate each patient's six-month reduction in HbA1c by interpolating/extrapolating from their assessments, given that their HbA1c levels were assessed on at least two occasions: baseline, and >3 months post baseline. Then, among patients with a sufficient number of occasions of HbA1c assessments, we will estimate their sixmonth HbA1c using generalized linear mixed models with patient-level random slopes and intercepts, with appropriate link function and distributional family [8]. The quantitative secondary analyses (Aims 1b-e, 2a-b) will use outcomes related to the longitudinal change in various metrics of glycemic variability (MAGE, C_v , range) as well as the frequency of hypoglycemic events, healthcare utilization, and cost. The secondary analyses will also use longitudinal data analysis to assess whether there is a significant reduction in glycemic variability over six months (Aims 1b-d) among those randomized to CGM, whether there is a significant reduction in hypoglycemic events over six months (Aim 1e) among those randomized to CGM, and to assess whether overall healthcare utilization and costs differ between randomized groups [9]. Accordingly, specific aims 1b-e will rely heavily on longitudinal data analysis within a multilevel/hierarchical framework [10], specifically using generalized linear mixed models. In the sensitivity analyses, provider variability will be accounted for using three-level (provider, patient, occasion), quasi-Bayesian generalized linear mixed models [11]. Finally, the sensitivity analyses exploring HTE will use generalized additive models (GAM) to identify subgroups of patients for whom CGM is likely to have a differential effect [12-13].

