2.0 STUDY OBJECTIVES/PURPOSE OF THE STUDY

The purpose of this study is to assess the effect of using CGM versus a standard of care (e.g. traditional fingerprick protocol) in an at-risk, diabetic patient population. The impact will be measured in terms of clinical outcomes (e.g., HbA1c level, glycemic variability), health care utilization (inpatient/outpatient visits), self-reported patient perceptions, and costs. We expect that CGM will empower patients to better manage their diabetes—ultimately, improving their health and reducing the burden of disease.

Figure 1

In this study, patients with type I and II diabetes will record their blood glucose levels since the output of the Dexcom G6 and the Contour Next ONE measure interstitial glucose. However, as noted in the *3.0 Study Design*, although the American Diabetes Association has provided a conversion table in which $\text{blood glucose} = 28.7 \times \text{A1C} - 46.7$ [6], the current standard of care is to have patients directly measure their blood glucose in the clinic rather than approximating. Thus, patients enrolled in this study will track their glucose with the general hypothesis being that those who more consistently monitor their blood glucose levels (and avoid the high peak to valley changes), will have a lower HbA1c at the end of the study. This will be tested by having HbA1c levels measured at two distinct time points: (1) at the time of enrollment, and (2) at the end of the pilot (six months). HbA1c levels may also be checked at the study midpoint (three months) if determined to be current standard of care by the provider and this data will also be considered. The aims below are written for HbA1c to confirm to the current standard of care.

Aim 1: Assess impact of CGM on glycosylated hemoglobin levels

Specific Aim 1a (primary analysis): Measure the effect of CGM vs. standard finger-prick protocol on HbA1c

- **Hypothesis for Aim 1a:** The patient-level six-month reduction in HbA1c will be greater among those randomized to CGM than that among those randomized to standard finger-prick protocol.
- **Process for Aim 1a:** We will compare the distributions of the patient-level, six-month change in HbA1c between randomized groups using the two-sided Wilcoxon rank-sum test.

Specific Aim 1b: Measure the longitudinal change in mean amplitude of glycemic excursion (MAGE) in CGM

- **Hypothesis for Aim 1b:** The patient-level daily MAGE will decrease over six months of CGM.

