3.0 STUDY DESIGN

This is a pilot, parallel randomized controlled trial of CGM versus a standard finger-prick protocol among patients with type I and II diabetes treated at Intermountain Healthcare’s Reimagine Primary Care Clinics. Patients will

be eligible if their most recent HbA1c level is $\geq 6.5\%$ and they are either currently using a glucose meter or are prescribed a glucose meter at their index encounter. Upon consent, which will occur within in a private office/room within the Reimagine Care Clinic, patients will be randomized into one of two groups:

- **Intervention group:** CGM using a Dexcom G6 to measure glycosylated hemoglobin levels every five minutes. Patients will be asked to download the Dexcom G6 and Clarity applications (to have access to their real-time data) and be given a link to complete an exit survey in REDCap near the end of their study participation. Data will be sent via Bluetooth and then exported by the Intermountain research team into a Tableau (or similar) dashboard for data analysis/comparison (**Appendix A**)
- **Control group:** A standard finger-prick protocol that will require patients to continue with their daily fingerprick regimen established by their physician. This group will be given a Contour Next One meter to ensure that each patient is receiving the same level of accuracy by the same device. A review by Ekhlaspour et al of 17 glucose meters demonstrated wide variability, with only two devices achieving the 2013 ISO standard (with the most accurate being the Contour Next) [7]. Patients in the control group will be asked to download the Contour Next application which will send data via Bluetooth similar to above. Data will be aggregated, and protected health information removed prior to analysis (by Intermountain Healthcare and Savvysherpa). At the end of the study, patients will be asked to complete a short survey in REDCap about their willingness to participate in future studies (**Appendix A**).

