3.1 Study Duration

This study will be conducted from 1 November 2018 through 31 December 2019 (13 months). This will allow sufficient time for study preparation (November 2018; 1 month), enrollment (approximately 3 months, starting December 1, 2018), follow-up (approximately 6 months from the time the last patient is consented), analysis (August 2019 – September 2019; 2 months), delivery of a final report to the Intermountain Healthcare Executive Leadership Team and co-authoring a manuscript for submission in a high-impact, peer-reviewed journal (October 2019 – December 2019; 2 months).

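### Aims 1b-1d test a trend in the CGM arm alone, with no pre-CGM or control series, so they describe change during CGM use and cannot show an effect or benefit of CGM

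*Combined protocol and SAP*

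**What the plan says.** Section 2.0 restricts all three aims to one arm. For MAGE: "Thus, among CGM patients only, we will measure the six-month longitudinal change in 24-hr average MAGE". For the coefficient of variation: "Thus, among CGM patients only, we will measure the six-month longitudinal change in daily C_v of blood glucose using the standard equation". For range: "So, among CGM patients only, we will measure the blood glucose range for the i th day". The reason given is that these metrics need near-continuous readings, which finger-pricks do not supply. The hypotheses concern change during use; for Aim 1b it is "The patient-level daily MAGE will decrease over six months of CGM". The method is a generalized linear mixed model giving an overall six-month trend, whose shape is not stated. Section 7.1 turns this into a test of "whether there is a significant reduction in glycemic variability over six months (Aims 1b-d) among those randomized to CGM".

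On the starting point, Section 3.3 has the coordinator hand over the device once the patient is randomized, and Section 3.3.2 excludes current CGM users. For the CGM arm Section 3.0 adds: "Patients will be asked to download the Dexcom G6 and Clarity applications (to have access to their real-time data").

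On framing, Aims 1b-1d stand under an Aim 1 headed as assessing the impact of CGM on glycosylated hemoglobin. Section 7.0 says that this impact will be evaluated both between and within randomized groups. It then plans, for every one of the listed aims, exploratory analyses of treatment-effect heterogeneity, to find subgroups in whom the benefit of CGM is larger or smaller.

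For Aim 1e, Sections 2.0 and 7.0 define a comparison between randomized arms. Section 7.1 speaks of a reduction in hypoglycemic events among CGM patients.

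**The concern.** An effect of CGM on glycemic variability is the difference between variability with CGM and variability without it. Aims 1b-1d observe only the first. The first recorded value is already on intervention, so a fitted trend compares later CGM use with earlier CGM use. It contains whatever part of the CGM effect builds up after the first usable day, plus every other change over the same six months, and the data cannot split the two.

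Two misreadings follow. A downward trend may be reported as benefit when it is background change. A flat trend may be reported as no benefit when the change came early. The heterogeneity analyses inherit the problem: a subgroup with a steeper trend in one arm is not a subgroup with a larger treatment effect.

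**Working it through.** **1. The plan's own figures.** Section 7.2 gives 125 enrolled, 20% attrition and 100 analysed: 125 × 0.80 = 100. With 50 per arm (1:1 assumed; the ratio is not stated), a difference of 1 and an SD of 1.25, two-sided 5% power is about 98%, consistent with the stated lower bound of 80%. These figures concern Aim 1a only. No effect size, SD or power is given for Aims 1b-1d, so what follows is illustrative.

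**2. What the trend contains.** Let E(t) be the CGM effect t days after the start and B(t) the background change. Observed change from the first usable day t0 to day 180 is [E(180) − E(t0)] + [B(180) − B(t0)]. A pre-CGM value would restore E(t0). A control series of the same metric would remove any B common to both arms. Neither is planned.

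**3. Sources of B in the documents.**
- Season: Section 3.1 plans "enrollment (approximately 3 months, starting December 1, 2018"). Entry in about December-February plus six months means finishing in about June-August, so follow-up runs winter to summer for nearly everyone.
- Care begun at entry: Section 3.0 admits patients if "they are either currently using a glucose meter or are prescribed a glucose meter at their index encounter".
- Study contact: coordinators check in monthly (Section 4.2), and a diabetes specialist reviews CGM profiles and passes on concerns (Section 8.3).

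The documents do not say how large any of these is.

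**4. Illustration: early effect, straight line.** Assume a full drop of 1 building as 1 − exp(−t/τ), B = 0, and a least-squares line over T = 180 days. With u = τ/T and e = exp(−1/u), the fitted six-month change as a share of the full drop is 6u(1 + e) − 12u²(1 − e). For τ = 3: u = 1/60, so 0.1000 − 0.0033 = 0.097. For τ = 60: u = 1/3 and e = 0.0498, so 2.0996 − 1.2669 = 0.833.

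| τ (days) | Share shown |
|---|---|
| 3 | 10% |
| 7 | 22% |
| 14 | 39% |
| 30 | 67% |
| 45 | 79% |
| 60 | 83% |
| 90 | 81% (86% of the drop has occurred by day 180) |

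Using daily points from day 0 or day 1 moves these by about two percentage points at most. A drop complete before the first usable day gives a trend of zero.

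**5. Illustration: background trend, no CGM effect.** Assume 50 CGM patients, a two-sided 5% test on per-patient slopes, day-to-day SD 1.0, and between-patient SD of six-month change 0.5, 1.0 or 1.5 (arbitrary units). Chance of a significant decrease, by simulation (4,000 runs per cell):

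| Background decline | SD 0.5 | SD 1.0 | SD 1.5 |
|---|---|---|---|
| 0 | 2% | 2% | 2% |
| 0.3 | 96% | 52% | 28% |
| 0.5 | 100% | 92% | 63% |

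**6. Aim 1e, side by side.** Section 2.0 compares the arms on each patient's change in event intensity, and Section 7.0 lists Aim 1e among the between-group intervention effects. Section 7.1 says the secondary analyses will also assess a reduction within the CGM arm. The sections do not say which decides the aim.

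**The case against.** The plan already draws much of the distinction. Section 7.0 separates within-patient change in the CGM arm (Aims 1b-1d) from intervention effects between arms (Aims 1e, 2a, 2b). The titles of Aims 1b-1d speak of longitudinal change in CGM, while those of 1a, 1e, 2a and 2b speak of the effect of CGM against finger-prick. The single-arm restriction is explained, and these aims are secondary. All of that stands, and a purely descriptive reading is legitimate. It does not cover the umbrella heading, the statement that impact is assessed within groups, or the treatment-effect heterogeneity analyses planned for each aim.

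Some stronger readings are tempting but not supported:

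- A reader might infer that the plan fits one straight line and so will miss a real benefit. Section 2.0 states no shape for Aims 1b-1d; a linear change is specified only for Aim 1e. Section 3.0 ties the six-month duration to gradual behavioral change, and with slow build-up most of the drop would be seen even with a line.
- A reader might name regression to the mean as a cause of decline. Selection is on HbA1c of at least 6.5%, not on MAGE, coefficient of variation or range, and nothing in the documents shows that it would carry over.
- A reader might take Section 7.1 on Aim 1e as a flat contradiction. Its wording allows an additional within-arm analysis, so the passages need reconciling; deletion is not the only answer.

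**Conclusion.** The point holds as a limit on interpretation. Aims 1b-1d can describe how variability changes while patients use CGM. They cannot show that CGM caused the change, that it had no effect, or who benefits more. This rests on the stated design alone: one arm analysed, real-time display from the start, and no pre-CGM or control sensor series described.

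Its numerical size is not determinable from the documents. The percentages in the working depend on assumed build-up times, SDs, allocation and a straight-line fit. They show that error is possible in both directions, not that it will occur. The randomized primary comparison (Aim 1a) and the sample size are unaffected, so the change is worth making but does not put the trial's main conclusion at risk.

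**What to change.** 1. In Sections 2.0, 7.0 and 7.1, label Aims 1b-1d as descriptive time trends during CGM use. State that neither a decrease nor its absence is evidence for or against an effect of CGM. Rest effect claims on the randomized comparisons (Aims 1a, 1e, 2a, 2b). Whether hypoglycemic events found by two modes of monitoring are comparable in Aim 1e is a separate question.
2. In Section 7.0, limit the treatment-effect heterogeneity analyses to the aims that compare randomized arms.
3. Specify the time function for Aims 1b-1d and make it flexible: a spline, or an early and a later period reported separately. This makes an early change visible but does not supply the missing pre-CGM reference. A calendar-month covariate should not be relied on to remove background trend: within a patient, calendar and study time advance together, and only about three months of staggered entry separate them.
4. Reconcile the Aim 1e wording in Section 7.1 with Sections 2.0 and 7.0: the between-arm comparison is the test of the aim, and any within-CGM change is descriptive.

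Cost: edits to three sections and one model specification, with no new data, visits or patients. The downside is weaker secondary claims.
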